## Phase 2 - Test #1 (randomized)

This test session is represented by Phase 2 in Figure 1, where the patient is placed on HVNI therapy with the order-randomized next generation cannula designs. Phase 2 will follow four distinct segments: (1) baseline characterization, (2) therapy acclimatization, (3) therapeutic characterization, (4) patient and clinician assessment scores.

Baseline Characterization will be performed just prior to the therapy acclimatization segment of this Phase. If there is a reason the clinician does not deem the patient appropriate for the study, per inclusion/exclusion criteria, they may stop procedures during baseline characterization. Sitting down in a comfortable environment, the patient will be setup and prepared for the cannula testing with appropriate data recording devices. The patient will be ON current/home oxygen therapy at this time. While subject is at rest, the following data will be collected (see Table 1): RR, HR, BP, SpO2, TcPCO2 and RPD (Modified Borg scale 0-10). For the RPD, the clinician will record patient scores.

Therapy acclimatization (5 – 10 minutes) will be performed after the baseline characterization segment is complete, and in accordance to site SOC to maintain patient safety. The patient will be fitted with appropriately sized nasal cannula (not to exceed 50% occlusion of the nares).

- IF order-randomized to the Unicorn cannula, then use the FiO2 & one-half the Flow settings from Phase 1 as a reference for the Therapeutic Settings.
  - For nostril selection of Unicorn cannula: Ask the patient to state which nostril is easiest to breathe through. Use that nostril to place the Solo/Unicorn cannula.
- IF order-randomized to the Prosoft cannula, then use the FiO2 & the Flow settings from Phase 1 as a reference for the Therapeutic Settings.

After the designated FiO2/Flow settings are implemented and the patient is acclimatized, the following data will be collected (see Table 1): RR, HR, BP, SpO2, TcPCO2 and RPD (Modified Borg scale 0-10). For the RPD, the clinician will record patient scores. Patient perception assessment will also be evaluated at this time.

NOTE: Should the patient or clinician deem that the therapy is not providing a comparable relief of dyspnea, then after recording the data stated above, proceed to increase titration of the flow until relief of symptoms, with attention to TcPCO2. At this time, the therapy acclimatization segment should be repeated, and data will be appropriately recorded to account for this 'settings' adjustment. This is to understand any difference in cannula efficacy between legacy design and next generation cannula, designs.

Therapeutic Characterization will be performed 5-10 minutes after the therapy acclimatization segment is completed. This will provide the patient sufficient time to receive clinical effect of the HVNI therapy and become sufficiently comfortable with the therapy and cannula. Once the respiratory therapist or other clinician skilled in management of HVNI deems that the HVNI settings are having a therapeutic effect, the following data will be collected (see Table 1): RR, HR, BP, SpO2, TcPCO2 and RPD (Modified Borg scale 0-10). For the RPD, the clinician will record patient scores.

Patient & Clinician Perception Assessment will be performed by the clinician or therapist performing this phase's testing procedures. Immediately following the completion of this phase, as soon as possible, the continuous Visual Acuity Scale (VAS) will be completed for each of the five endpoints for clinician assessment and the two endpoints for the patient assessment. For the patient perception these include: (1) relief of symptoms, and (2) comfort/tolerance. For the clinician perception these include: (1) technical/clinical difficulties, (2) patient comfort & tolerance, (3) ease of use, (4) monitoring & support for therapy, and (5) expected/perceived patient outcomes.

**Upon completion of this phase**, the testing will pause for 15 minutes, until patient has returned to baseline dyspnea, prior to continuing with the next nasal cannula design test. During this pause the patient will not perform known to worsen dyspnea. During the pause the patient will continue with their current oxygen therapy.

Phase 3 - Test #2 (randomized)

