This study design will focus on four distinct segments for each phase: (1) baseline characterization, (2) therapy acclimatization, (3) therapeutic characterization, and (4) VAS for both patient and clinician assessment scores. The baseline characterization for Phase 1 will provide patient background, history, and initial clinical evaluation. For Phases 2 and 3, baseline characterization will only include the initial clinical evaluation, as no further initial evaluation is warranted. The acclimatization period will provide patients time to become accustomed to the HVNI therapy and both designs of nasal cannula design. Titration of therapy (Flow/FiO2) is only expected during Phase 1 (or in the event the patient decompensates and needs adjustment), the legacy cannula, as this study is a comparison of cannula efficacy. For the therapeutic characterization, final patient data for the cannula design will be recorded. Following this, the clinician and the patient will complete the cannula design's VAS perception scores. Primary and secondary outcomes will be completed at the end of each individual phase.

This study will be conducted in an inpatient hospital setting where patient testing can be performed with appropriate medical supervision and staff training to maintain patient safety. All respiratory interventions will be tracked during the study window for each patient.

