#### **VI. Study Procedures**

This study is non-blinded by necessity, since the difference in cannulas can be perceived by both the clinician and patient. Patients may not know the difference between legacy and next generation cannulae, except in case of the Unicorn cannula design (as it employs a single-nasal prong). The next generation cannulae will be order-randomized after the conventional legacy cannula is used during the control evaluation. The study is a crossover design trial that will measure the ventilatory and comfort performance of nasal cannula design, specifically the effect on relief of dyspnea as demonstrated by RPD assessment, and measurement by TcPCO2 device. In addition, patient physiologic outcomes (e.g. HR, RR, BP, SpO2), and patient & clinician assessment scores will be assessed and documented. Figure 1 illustrates a flowchart of overall study procedures.

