## VII. Data Collection

## Table 1. Key study data and collection points for each Phase of the Study.

	Baseline Characterization	Therapy Acclimatization	Therapeutic Characterization	@ Study End
Patient History & Health	Х			
Treatment: Flow & O2	Х	Х	Х	
Physiologic Parameters	Х	Х	Х	
Ventilation Parameters	Х	Х	Х	
Clinician Perception Scores			X	Х
Patient Perception Scores			Х	Х

Patient enrollment data collection will include patient history, health, demographics, and current respiratory therapies. Only Phase 1 will record the patients' history and background information. For each segment of each phase, the following data will be recorded for comparison:

Physiologic Parameters o SpO2, HR, RR, BP Ventilation Parameters o RPD, TcPCO2

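### End-of-phase dyspnea on a test cannula is read after any flow increase for poor relief, so it cannot by itself support comparability at the designated flow

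*Combined protocol and SAP*

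**What the plan says.** RPD is collected at baseline, acclimatization and therapeutic characterization in every phase. Section VII (Table 1 and the text below it) states: "For each segment of each phase, the following data will be recorded for comparison". Section II and the Primary Endpoint list in Section VII give the scale but no time point. Section VIII names a test but no reading, and does not say whether the score or the change from that phase's baseline is analysed.

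Section IV gives the only pointer: "Primary and secondary outcomes will be completed at the end of each individual phase", and "For the therapeutic characterization, final patient data for the cannula design will be recorded".

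Section VI, Phase 2, has each patient start a test cannula with the Phase 1 FiO2 and either the Phase 1 flow (Prosoft) or half of it (Unicorn). These settings are described as a reference. RPD is recorded at them after acclimatization. The NOTE then adds: "Should the patient or clinician deem that the therapy is not providing a comparable relief of dyspnea", staff are to, "after recording the data stated above, proceed to increase titration of the flow until relief of symptoms, with attention to TcPCO2". Acclimatization is repeated and therapeutic characterization follows. Phase 3 repeats these procedures.

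Section IV describes titration differently: "Titration of therapy (Flow/FiO2) is only expected during Phase 1 (or in the event the patient decompensates and needs adjustment". Section VI adds: "This study is non-blinded by necessity, since the difference in cannulas can be perceived by both the clinician and patient".

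**The concern.** A flow increase on a test cannula is triggered by the outcome itself. An unblinded patient or clinician, with no numeric threshold, judges that relief falls short. Flow then rises until it no longer does, and only afterwards is the end-of-phase RPD taken. Patients who look worse on the test cannula at the designated settings are moved toward parity, while those who look better are left alone.

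If extra flow lowers RPD, which is the purpose of the NOTE, the end-of-phase difference understates a true deficit at the designated settings and can show an advantage there that does not exist. For Prosoft, cannula effect is mixed with extra flow. For Unicorn, the reading no longer tests the designated half flow.

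The study aims to establish equivalence, while Section VIII specifies only tests of difference. A shrunken difference could therefore be read as comparability. With the reading not confirmed in the analysis section, it could also be chosen after the data are seen.

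**Working it through.** **Plan's own figure.** Section V gives a difference of 2, SD 3, 90% power and alpha 0.05, with N=26. The exact noncentral t calculation (paired, two-sided) gives power 0.892 at n=25 and 0.904 at n=26, so 26 is reproduced. At SD 2, the lower end of the protocol's range, power is 0.998.

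**Model (assumed, not in the documents).**
- D is test minus legacy RPD at the designated settings, normal with mean μ and SD σ. The bounded 0-10 scale makes this an approximation.
- The late difference without re-titration has the same mean and SD, and correlation ρ with D.
- A fraction f of patients with D of 2 or more is re-titrated.
- Titration removes a share k of the persistent part, μ + ρ(D − μ).

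End-of-phase mean = μ − k·f·[μ·P(D≥2) + ρ·σ·φ(z)], with z = (2 − μ)/σ and φ the standard normal density.

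**True deficit 2, SD 3, f=0.5.** Here z=0, P=0.5 and φ=0.399, so 25% are re-titrated. For ρ=1 and k=1 the mean is 2 − 0.5·(1 + 1.197) = 0.90. Power is from simulation (40,000 trials of n=26, paired t-test):

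| ρ | Mean, k=1 | Power, k=1 | Mean, k=½ | Power, k=½ |
|---|---|---|---|---|
| 1 | 0.90 | 0.41 (0.32 if fresh SD 3 noise remains after titration) | 1.45 | 0.79 |
| 0.5 | 1.20 | 0.51-0.54, depending on residual noise | 1.60 | 0.77-0.79 |
| 0 | 1.50 | about 0.65 | 1.75 | 0.81 |

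The signed-rank test behaves alike: in the most severe case power falls from 0.89 to 0.31. At SD 2 the t-test falls from 0.998 to about 0.75-0.92 (k=1) or about 0.99 (k=½).

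**Fewer re-titrated.** With f=0.2, 10% are re-titrated. The mean for ρ=1, k=1 is 2 − 0.2·2.197 = 1.56, and power at SD 3 is about 0.72-0.87 across the cases.

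**No true difference, SD 3, f=0.5, k=1.** Here z=0.667, P=0.252 and φ=0.319, so 12.6% are re-titrated. The mean is −0.5·ρ·3·0.319, which is −0.48, −0.24 or 0 for ρ = 1, 0.5 or 0. The test cannula appears significantly better at the designated settings in about 15%, 6% or 2.5% of trials; the nominal rate is 2.5%. At SD 2 the highest figure is about 10%.

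**Mixing readings.** Using early readings for re-titrated patients and late readings for the rest reverses the error. With no true difference, ρ=0.5 and SD 3, the mean is 0.48·(1 − 0.5) = +0.24, a false deficit.

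**Flow.** Phase 1 targets are 20 to 35 L/min (up to 40). Half is 10 to 17.5 (20) L/min, so a Unicorn patient can have flow raised by that much before reaching the Phase 1 level.

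**Time on cannula.** The early reading follows 5-10 minutes. The end-of-phase reading follows 10-20 minutes (5-10 plus 5-10), or 15-30 if acclimatization is repeated.

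**The case against.** The strongest reply is that the plan has a reading and a sensible question. Section IV points to the end of the phase, and of that segment's interval Section VI says: "This will provide the patient sufficient time to receive clinical effect of the HVNI therapy". Legacy flow is titrated for relief in Phase 1 before its own readings, so poor relief on legacy is corrected too and the end-of-phase comparison sets titrated against titrated. The designated settings are only a reference. The NOTE requires RPD before the increase, and Table 1 captures flow in each segment, so nothing is lost.

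Most of this stands. A reader might infer that the primary reading is wholly undefined, that the end-of-phase comparison is invalid, or that only the test cannula benefits from titration. The documents support none of these. Nor is the Unicorn question about lower flows lost whenever flow is raised: it is lost only if flow reaches the Phase 1 level.

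The pre-increase reading is also imperfect. It comes before the interval just quoted, and sets individually titrated legacy settings against unadjusted test settings. Choosing between the readings is the sponsor's choice of question.

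The reply does not supply a rule for re-titrated patients or any text linking the recorded early deficit to the conclusion. Titrated against titrated does not show comparability at equal or half flow.

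**Conclusion.** The point holds in limited form and should be fixed. The end-of-phase RPD is a fair measure of relief after titration. It is biased toward the test cannula as evidence of comparability at the Phase 1 flow (Prosoft) or half of it (Unicorn), and the plan does not separate the two claims.

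The direction rests on extra flow lowering RPD. The size cannot be determined: the trigger threshold, the share re-titrated, the effect of titration and the persistence of early differences are all absent, and Section IV expects little titration. A reader might take the lowest power figure, or the 15% false-advantage rate, as the expected effect. Each is the severe end of an assumed range. If early differences do not persist there is no false advantage when the cannulas are truly equal.

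Because both readings and flow are already collected, this is a gap in the definition and analysis of the outcome, not a failure of data collection.

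**What to change.** Leave clinical titration unchanged and amend Sections IV, VII and VIII:

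1. Name one primary RPD reading, the same for every patient and cannula, and say whether it is the score or the change from that phase's baseline.
2. Base any claim at the same or half flow on the acclimatization RPD recorded before any flow increase (for legacy, the acclimatization reading at the final Phase 1 settings). State its limits: shorter exposure, and titrated legacy against unadjusted test settings.
3. Report end-of-phase RPD per cannula with final flow and the proportion needing a flow increase. Limit conclusions from it to relief after titration, including if it is kept as primary.
4. Do not combine early readings for some patients with late readings for others.
5. The sponsor should reconcile the titration wording in Section IV with the NOTE under Phase 2. Section IV states an expectation, not a prohibition, but the triggers differ.

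The cost is wording and one extra set of summaries, with no added visit or measurement and no change to N=26. Recording minutes at settings with each reading would help, since exposure is unequal either way.

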# For Phase 3, go back and repeat all procedures from Phase 2 with the difference of testing the second randomized cannula (Prosoft or Unicorn).

**Upon completion of this phase**, the study testing procedures will be deemed completed, and any final study data will be finished at this time. At this time, the patient may resume current/home oxygen therapy.

## **Other Medical Care**

All other medical treatment will remain the purview of the attending physician and will be administered in accordance with clinic standards. This study is designed to evaluate only the patients' ventilatory performance, oxygenation, and physiologic parameters while on HVNI with current and next generation cannula designs. It is assumed that the ancillary interventions will adhere to common clinical practice guidelines and conventions. All treatments given to subjects will be documented on their CRFs.

## VII. Data Collection

## Table 1. Key study data and collection points for each Phase of the Study.

	Baseline Characterization	Therapy Acclimatization	Therapeutic Characterization	@ Study End
Patient History & Health	Х			
Treatment: Flow & O2	Х	Х	Х	
Physiologic Parameters	Х	Х	Х	
Ventilation Parameters	Х	Х	Х	
Clinician Perception Scores			X	Х
Patient Perception Scores			Х	Х

Patient enrollment data collection will include patient history, health, demographics, and current respiratory therapies. Only Phase 1 will record the patients' history and background information. For each segment of each phase, the following data will be recorded for comparison:

Physiologic Parameters o SpO2, HR, RR, BP Ventilation Parameters o RPD, TcPCO2

## **Primary Endpoint**

• Modified Borg scale score(s) -Rated Perceived Dyspnea (RPD)

## Secondary Endpoints

- Physiologic parameter(s) SpO2, HR, RR, BP
- Ventilation parameter(s) –TcPCO2

## **Tertiary Endpoints - Patient & Clinician Assessments**

- Patient Assessment
  - Patient assessment of respiratory response to therapy, ranging from Insufficient to Excellent Response, as continuous VAS.
  - Patient assessment of comfort and tolerance of the therapy, ranging from Insufficient to Excellent as continuous VAS.
- Clinician Assessment
  - Clinician assessment of patient respiratory response to therapy, ranging from Insufficient to Excellent Response, as continuous VAS.
  - Clinician assessment of frequency of rain-out, interface slippage or other technical/clinical difficulties applying therapy, ranging from Never to Frequent as continuous VAS.

- Clinician assessment of patient comfort and tolerance of therapy, ranging from Insufficient to Excellent as continuous VAS.
- Clinician assessment of simplicity of set-up and use, ranging from Complex to Setup and Use to Simple to Setup and Use, as continuous VAS.
- Clinician perception of Monitoring and support of therapy required (adjustments, refilling fluids, adjusting interface), ranging from Minimal to Frequent, as continuous VAS.

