## IV. Study Design

This will be an efficacy study, performed as a prospective, order-randomized crossover design trial to evaluate the ability of next generation HVNI nasal cannula designs (Unicorn and Prosoft) to effect ventilation and related physiological responses relative to the conventional legacy cannula design. Patients deemed to fit the criteria for inclusion will perform the study procedures for both arms of the crossover design. Completing both arms will compare the next generation cannula designs to the commonly used legacy design for comfort, comparative therapeutic response, and outcomes per the study aims. Patients are expected to complete the study in one session, with appropriate pauses between each nasal cannula design testing procedures. After each of the study arms, the clinicians will complete perception score assessments. The clinical management will otherwise remain unchanged based on site standard of care practice.

Each phase of the study will correspond to a different cannula design. Patients will be enrolled and initially entered into the control/baseline phase with the conventional legacy cannula (control), then will be order randomized to either of the next generation cannula designs (Test: Unicorn, or Prosoft).

- Phase 1 – Conventional Legacy cannula design (Control)

- Phase 2 Next generation cannula design (Test#1) (order randomized)
- Phase 3 –Next generation cannula design (Test#2) (order randomized)

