## Phase 1 - Conventional Legacy cannula design (Control)

This test session is represented by Phase 1 in Figure 1, where the patient is placed on HVNI therapy with an appropriately fitted conventional legacy cannula design. Phase 1 will follow four distinct segments: (1) baseline characterization, (2) therapy acclimatization, (3) therapeutic characterization, (4) patient and clinician assessment scores. After Phase 1 is completed the next generation cannula test #1 will be able to start, as deemed appropriate by the clinician.

Baseline Characterization will be performed just prior to the therapy acclimatization segment of this Phase. If there is a reason the clinician does not deem the patient appropriate for the study, per inclusion/exclusion criteria, they may stop procedures during baseline characterization. The inpatient may be sitting or lying down in a comfortable environment. The patient will be set up and prepared for the cannula testing with appropriate data recording devices. While subject is at rest, the following data will be collected (see Table 1): RR, HR, BP, SpO2, TcPCO2 and RPD (Modified Borg scale 0-10). For the RPD, the clinician will record patient scores. The patient may or may not be on HVNI therapy at this time. The Phase 1, baseline characterization will include recording data while the patient is in an uncompromised state (e.g. ON current oxygen therapy, if applicable).

Therapy acclimatization (5 – 10 minutes) will be performed immediately after the baseline characterization segment is complete, and in accordance with site standard of care practices to maintain patient safety. The patient will be fitted with appropriately sized nasal cannula from the conventional legacy design (not to exceed 50% occlusion of the nares). Patients will be notified of best practice for the therapy, and clinicians will record whether patients prefer to keep their mouths open or closed. The acclimatization segment is the interval during which HVNI is to be titrated to provide the patient the appropriate settings for effective HVNI therapy. After the final FiO2/Flow settings are implemented and the patient is acclimatized the following data will be collected (see Table 1): RR, HR, BP, SpO2, TcPCO2 and RPD (Modified Borg scale 0-10). For the RPD, the clinician will record patient scores. Effective flow is recorded.

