HVNI will be initiated per the initial settings identified below, after which settings will be titrated per standard practice for optimal effect. When patients are placed, the HVNI initial settings will be the following: FiO2 = level approximating the patient's prior prescription (e.g. if by nasal cannula [NC], 1LPM NC = 24%, 2LPM NC = 28%, 3LPM NC = 32%, etc.), Flow = 15 L/min, and Temperature = 35 - 37°C. Patients will be fit with a Vapotherm adult nasal cannula that will be applied by a respiratory therapist or other clinician skilled in management of HVNI. The flowrate can be decreased or increased as rapidly as necessary to alleviate respiratory distress and optimize patient comfort. Targets should be to provide relief of perceived dyspnea at an HVNI flow rate between 20 to 35 L/min (up to 40L/min). Starting temperature will be between 35 to 37°C; if patients find the gas temperature to be uncomfortable, it can be lowered as necessary down to 33 °C to enhance tolerance. The FiO2 will be set initially to approximate the likely previous dosage (see above) to initially to assure adequate oxygenation, but this should be adjusted to maintain a SpO2 > 88%.

Therapeutic Characterization will be performed 5-10 minutes after the therapy acclimatization segment is completed. This will provide the patient sufficient time to receive clinical effect of the HVNI therapy and

become sufficiently comfortable with the therapy and cannula. Once the respiratory therapist or other clinician skilled in management of HVNI deems that the HVNI settings are having a therapeutic effect, the following data will be collected (see Table 1): RR, HR, BP, SpO2, TcPCO2 and RPD (Modified Borg scale 0-10). For the RPD, the clinician will record patient scores.

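### The clinician monitoring-and-support score is confounded with phase: it names adjustments, and the protocol builds titration into the legacy phase

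*Combined protocol and SAP*

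**What the plan says.** Section VII (Tertiary Endpoints) lists two patient and five clinician VAS items. One clinician item is "Clinician perception of Monitoring and support of therapy required (adjustments, refilling fluids, adjusting interface), ranging from Minimal to Frequent, as continuous VAS". Another is "Clinician assessment of simplicity of set-up and use, ranging from Complex to Setup and Use to Simple to Setup and Use, as continuous VAS". They are scored phase by phase: "After each of the study arms, the clinicians will complete perception score assessments" (Section IV). Each score therefore belongs to one cannula.

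The order is only partly randomized. Section IV states "Patients will be enrolled and initially entered into the control/baseline phase with the conventional legacy cannula (control"; only Unicorn and Prosoft are then randomized in order.

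Titration is assigned by phase. Section IV states "Titration of therapy (Flow/FiO2) is only expected during Phase 1 (or in the event the patient decompensates and needs adjustment". Under Phase 1, Section VI states "The acclimatization segment is the interval during which HVNI is to be titrated to provide the patient the appropriate settings for effective HVNI therapy". HVNI starts at 15 L/min and "Targets should be to provide relief of perceived dyspnea at an HVNI flow rate between 20 to 35 L/min (up to 40L/min". FiO2 is adjusted to keep SpO2 above 88%.

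In the test phases, Prosoft is to "use the FiO2 & the Flow settings from Phase 1" as its reference, and Unicorn takes the Phase 1 FiO2 with half the Phase 1 flow. A NOTE under Phase 2, which also governs Phase 3, calls for raising the flow and repeating acclimatization when relief is not judged comparable.

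Section VIII applies a signed-rank test at 0.05 (a t-test if the data are normal) to all applicable variables, with no term for phase or titration.

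**The concern.** The item is meant to show how much support each cannula needs. Its wording invites the clinician to include setting changes, and the protocol plans those changes for the legacy phase. Nothing in Sections VI to VIII tells the rater to leave protocol-required titration out. Because legacy never appears in another phase, no analysis of these scores can separate the cannula from the titration.

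Monitoring and support is a named Aim 3 endpoint. If Prosoft were found to need less support than legacy at the 0.05 level, part or all of that result could come from the protocol's own sequence.

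**Working it through.** **The plan's own figure.** The only sample-size figure is for the primary Borg endpoint: difference 2, SD 3, power 90%, alpha 0.05. With d = 2/3 and a two-sided exact paired t-test, the noncentrality at n = 26 is (2/3) × √26 = 3.40 and power is 0.904. Since 26 is the smallest n reaching 0.90, the stated N reproduces; 26 × 1.20 = 31.2, rounded up to 32, matches the enrolment cap. The plan gives no such figure for the VAS items.

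**Planned flow changes if all three cannulas were identical** (inputs from Section VI, Phases 1 and 2):

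- Legacy: the rise needed to enter the target range is 20 − 15 = 5 L/min; to its top, 35 − 15 = 20 L/min. Reaching the target takes at least one flow change.
- Prosoft: it starts at the final legacy flow, so the planned change is 0.
- Unicorn: it starts at half the final legacy flow. Legacy finals of 20, 25, 30, 35 and 40 L/min give starts of 10, 12.5, 15, 17.5 and 20 L/min, at or below the bottom of the 20 to 35 range. A Unicorn identical to legacy could therefore trigger the NOTE and need as many changes as legacy, or more.

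For Prosoft the adjustments component runs against legacy. For Unicorn the effect could shrink, vanish or reverse.

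**What an artifact could do to the test.** The documents give no VAS shift or SD, so this is an illustration under assumptions. Let Phase 1 titration shift the legacy score by d SDs of the paired difference, with no true cannula difference, n = 26 and a two-sided 0.05 test (sidedness is not stated in Section VIII). Let a fraction f of test phases be re-titrated, with the same shift. The entries are signed-rank rejection rates from 4,000 simulated trials with normal paired differences:

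| Assumed d | f = 0 | f = 0.25 | f = 0.5 | f = 0.75 | f = 1 |
|---|---|---|---|---|---|
| 0 | 0.048 | 0.046 | 0.051 | 0.048 | 0.048 |
| 0.2 | 0.156 | 0.116 | 0.078 | 0.056 | 0.048 |
| 0.3 | 0.297 | 0.194 | 0.114 | 0.068 | 0.048 |
| 0.5 | 0.665 | 0.419 | 0.222 | 0.098 | 0.046 |
| 0.8 | 0.969 | 0.780 | 0.432 | 0.140 | 0.050 |

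The exact t-test (noncentrality d√26, 25 degrees of freedom) gives 0.165, 0.313, 0.688 and 0.975 at f = 0 for the four nonzero shifts, in line with the first column. The table does not cover a test phase that needs more adjustment than legacy, which is possible for Unicorn.

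**The case against.** Four points on the other side have force.

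1. *The item is not a count.* It is an overall perception, with adjustments as one of three bracketed examples. A clinician might discount planned titration unprompted. The CRF and any rater guidance are not among the documents and may already deal with this. This stands as a limit on size; it does not remove the confounding in the item as the protocol words it.

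2. *Direction.* A reader might infer that the score favours both new cannulas. The documents do not support that. Unicorn's half-flow start and the NOTE leave its direction open. Prosoft can also be re-titrated under the NOTE, but for an identical cannula at the same flow nothing planned calls for it.

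3. *The set-up item.* A reader might infer that it is biased equally, on the view that only legacy includes starting HVNI. Section VI says otherwise: patients return to their current oxygen therapy in each pause, so HVNI is restarted in every phase. Some patients may already be on HVNI at the Phase 1 baseline. Unicorn also has a nostril-selection step that legacy lacks. At most, the work of finding the settings differs.

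4. *The rejection rates.* They follow from assumed shifts and would look the same for any artifact of that size. They fall quickly as test phases are re-titrated and return to about 0.05 when all are. They show what could happen and do not estimate this trial's error rate.

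**Conclusion.** The point holds in a limited form. For Prosoft versus legacy, the adjustments component is confounded with phase and tends to count against legacy. For Unicorn versus legacy, the contrast is confounded with unknown direction. This rests on two assumptions: that raters give some weight to protocol-required titration, and that no guidance outside the protocol tells them not to.

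The size cannot be derived from the documents. In the illustration, the chance of a spurious finding at n = 26 ranges from about 5% to 97%, depending on the assumed shift and on how often test phases are re-titrated.

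The reach is small: one of seven tertiary VAS items, with a possible minor effect on a second. The primary Borg endpoint and the secondary endpoints do not use this score. The correction is worth making because it is nearly free.

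**What to change.** In Section VII and on the CRF:

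- Have the monitoring-and-support item scored, in every phase alike, only for support needed after that phase's final settings are established. In a test phase re-titrated under the NOTE, that means after the increase.
- Tell raters to leave settings-finding out of the set-up item.
- Report flow and FiO2 changes made before that point, both Phase 1 titration and increases under the NOTE, separately by phase. Table 1 already records flow and oxygen at each segment.

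For scores already taken on the current item wording, report the legacy contrasts on the monitoring-and-support item as descriptive, without a 0.05 test. Prosoft versus Unicorn is not a clean substitute, because the protocol starts those two at different flows.

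Section IV and the Phase 2 NOTE must also be reconciled. The former expects titration outside Phase 1 only on decompensation, while the latter calls for it when relief is not judged comparable.

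The cost is a few lines of protocol and CRF wording, with no new visit or patient and no change to clinical management. The downsides are that the item no longer captures total bedside workload, and scores on the two wordings are not directly comparable. The change removes the titration artifact only; legacy would still always come first.
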